## 3.2 Randomization

The study will be conducted in five distinct US geographical areas in each of which a minimum of 12 primary care clinics will be participating and enrolling patients. The unit of cluster randomization will be the primary care clinic site. Thus, in one geographical area, six PCP clinics will be randomized to the GBC arm and six to the GBC+PIPT arm. The unit of randomization and analysis is a cluster because the intention is to enhance the application of a stratified approach to treating LBP in primary care environments as a whole while minimizing contamination. When randomization at the individual level was considered, it was found to be impractical and susceptible to selection bias and contamination.

The randomization for each study site will be conducted by the study biostatistician and will be stratified by two factors: Total Back Pain Encounters (Factor 1) and % Medicaid/Self-Pay (Factor 2). First, the clinics will be ordered by Factor 1 and divided into subgroups (blocks). Clinics in each block will then be further ordered by Factor 2, and randomly assigned to either group A or group B, making sure that the two groups would be balanced in terms of both Factor 1 and Factor 2.

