### 3.4 Study population and sites

The target population for this study will be adult patients who present to primary care physicians (i.e., internal medicine, family practice, and geriatric medicine physicians) with a primary complaint of LBP. Patients will be recruited from health systems in five regional areas that surround: 1) Pittsburgh, PA (UPMC); 2) Boston, MA (Boston Medical Center); 3) Baltimore, MD (Johns Hopkins Medicine); 4) Charleston, SC (Medical University of South Carolina); and 5) Salt Lake City, UT (Intermountain Healthcare). Within the individual regional areas, primary care clinics have been identified that represent community-based PCP clinics. In all instances, there are more potential sites than are required for successful completion of the trial, which will allow flexibility in the randomization scheme and alternatives should there be individual PCP-clinic recruitment shortfalls. This large, nation-wide group of clinics across five different health systems provides a high level of pragmatism for the PRECIS-2 organizational domain because the systems will be variable with regards to provider expertise, resources, and organizational structure.

Certain patient subgroups are of particular interest (**SA5**) given greater risk for poorer LBP outcomes as demonstrated in observational cohort studies. Adequate enrollment will be assured to have statistical power to conduct subgroup analyses of patients with lower socioeconomic status (using insurance as a proxy) and the comorbid conditions of smoking, depression, and obesity. Identification of subgroups will be based on information obtainable in the EMR. The participating primary care clinics will be sampled to reflect gender, race, and ethnicity proportions of the population being served at the recruitment sites.

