## 9.5 Data analyses

- 9.5.1 **Primary outcome 1:** This initial analysis (**PA1**) will use a generalized linear mixed model with a logit link controlling for block set (see Randomization) and a fixed effect for intervention accounting for the cluster RCT design with a random clinic effect. Primary analyses will also adjust for patient characteristics (maladaptive pain coping behaviors such as catastrophizing and fear avoidance, functional impairment as measured by the Oswestry, and presence

of psychiatric comorbidities), as these have been associated with higher transition to chronic LBP. The intraclass correlation coefficients will also be estimated and reported for all outcome measures to assess the assumptions for sample size analyses and also for future investigations using similar designs and outcomes. Analysis for the secondary aims (**SA4** and **SA5**) will be largely descriptive assessing the proportion of patients who transition to chronic LBP among the low and moderate risk observational cohort. The proportion and confidence interval will be estimated using generalized linear models adjusting for clustering.

- 9.5.2 **Primary outcome 2:** This aim (**PA1**) will be analyzed using contrasts from a linear mixed models analysis for 6-month back-related function (Oswestry) controlling for baseline Oswestry and the block set (see Randomization). The intervention will first be explored by time interaction, and then proceed to a main effects model with only group and time. For the secondary aims (**SA4** and **SA5**) patient-centered outcomes, such as functional status, would use general linear models if deemed appropriate based on normality assumptions. If normality is hugely violated, a cutpoint for 'response' will be applied.

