- 9.5.3 **Secondary outcome:** Analyses of health care utilization data (**SA3**) will use generalized linear mixed models with the distribution determined by the type of data but still controlling for the cluster randomized trial design by having random effects for clinics. Logit link (binary distribution) will be used for health care outcomes, such as surgery, that are dichotomous (Yes/No) variables. For outcomes resulting in count data over the time frame such as number of outpatient visits for back pain, hospitalizations or ER visits, Poisson or negative binomial distribution with log link will be used to compare the event rates controlling for the period of follow up. The secondary aims (**SA4** and **SA5**) would use a similar approach.

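### The SA3 utilization models in 9.5.3 name no block-set or health-system term, although the randomization is blocked within site and both primary models adjust for block; adding it protects the precision of H3 at almost no cost.

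*Combined protocol and SAP*

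**What the plan says.** Section 3.2 makes the clinic the unit of randomization and blocks it within site: "The randomization for each study site will be conducted by the study biostatistician and will be stratified by two factors: Total Back Pain Encounters" and share of Medicaid or self-pay patients. Clinics are ordered by back pain volume, divided into blocks, ordered within block by payer mix, and then allocated. Because this is done site by site, the block set identifies the health system, the volume stratum and part of the payer mix.

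The three analysis paragraphs in 9.5 then differ:

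- 9.5.1 (PA1): "controlling for block set (see Randomization) and a fixed effect for intervention accounting for the cluster RCT design with a random clinic effect". Block set and the random clinic effect are two separate terms.
- 9.5.2 (PA2): a linear mixed model "controlling for baseline Oswestry and the block set (see Randomization").
- 9.5.3 (SA3): generalized linear mixed models "still controlling for the cluster randomized trial design by having random effects for clinics". The only other covariate named is follow-up time, for counts: "Poisson or negative binomial distribution with log link will be used to compare the event rates controlling for the period of follow up".

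No other section supplies a block or site term for SA3. Section 9.2.5 provides for adjustment only where baseline differences are observed, and only in sensitivity analyses. Section 10.1.3 limits the utilization data to four of the five sites.

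**The concern.** A model that reflects a blocked cluster randomization needs both the clinic effect and the blocks. The primary models have both; the SA3 paragraph, which says it controls for the same design, names only the clinic effect. Because arms are balanced within block, differences between blocks cancel out of the arm contrast. A model without a block term does not know this. It counts those differences as random clinic-to-clinic variation and widens the standard error accordingly.

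The documents give some reason to expect differences between systems: in 3.4, "the systems will be variable with regards to provider expertise, resources, and organizational structure", and 2.3.5 mentions shared-savings and quality programs at three of the four systems that supply SA3 data. At stake is precision for H3, which rests on four sites and has no stated power.

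**Working it through.** **Step 1: the plan's own figures.** The plan states no power for SA3, so there is nothing to reproduce for H3. The PA1 figure in 9.2.3 (just over 80%) does reproduce, taking two-sided alpha 0.05 and effective n per arm = 30n / [1 + (n − 1) × 0.05]:

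- 25% vs 15%, n = 14: 420 / 1.65 = 254.5 per arm, power 80.7%.
- 30% vs 18%, n = 10: 300 / 1.45 = 206.9 per arm, power 81.8%.

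This confirms how the plan treats clustering but says nothing about utilization.

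**Step 2: inputs for SA3.**

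- Clinics: 4 sites (10.1.3) × a minimum of 12 (3.2) = 48.
- High risk patients per clinic: m = 31 (9.2.2), taken as equal.
- ICC: none is given for utilization. The documents use 0.05 for PA1, described as an upper bound for pain and LBP outcomes (9.2.3), and 0.01 for the observational cohort (Table 3). Both are tried.
- Block size: not stated; blocks of 4, split 2:2, are assumed.
- Share R of between-clinic variance due to system and block: not stated; 0 to 70% is tried.

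**Step 3: the standard error.** Set total variance to 1. The variance relevant to a clinic mean is

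- without a block term: V0 = ICC + (1 − ICC)/31
- with a block term: V1 = (1 − R) × ICC + (1 − ICC)/31

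The true variance of the arm difference is (4/48) × V1 under either model, because block effects cancel. The model without block estimates roughly (4/48) × V0, so its standard error is too large by about √(V0/V1).

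- ICC 0.05: V0 = 0.05 + 0.95/31 = 0.0806. For R = 30 / 50 / 70%, V1 = 0.0656 / 0.0556 / 0.0456, giving ratios of 1.11 / 1.20 / 1.33.
- ICC 0.01: V0 = 0.01 + 0.99/31 = 0.0419. V1 = 0.0389 / 0.0369 / 0.0349, giving ratios of 1.04 / 1.07 / 1.10.

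**Step 4: power.** Clinic means were simulated under a normal approximation, with the effect set so that the block-adjusted test has 80% power. The block-adjusted test has 35 df and the test without block 46 df.

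| Share R | Power without block, ICC 0.05 | Power without block, ICC 0.01 |
|---|---|---|
| 0% | about 81% | about 81% |
| 30% | about 75% | about 78% |
| 50% | about 70% | about 77% |
| 70% | about 62% | about 75% |

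Repeat runs move these by a point or two; at ICC 0.05, R = 50% gave 68 to 70% and R = 70% gave 60 to 62%. Type I error without block at ICC 0.05 was about 3.0 / 2.4 / 1.6% for R = 30 / 50 / 70%, so the test errs on the conservative side.

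**Step 5: sensitivity.**

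- Clinic sizes varying with the plan's CV of 0.65 (9.2.2), ICC 0.05: power without block 75 / 69 / 62% for R = 30 / 50 / 70%, against 78 to 80% with block. Unequal sizes do not remove the loss.
- Health system alone as the fixed effect, same setting: 78 / 75 / 73%, roughly half or more of the loss recovered. How much depends on how the variation splits between system and block.
- 15 patients per clinic, ICC 0.05, R = 50%: power without block 74.2%, so the loss is smaller. This matters because 3.1.1 says resource use is evaluated in only a subset of patients.
- R = 0: including block costs under 1 point with blocks of 4 and 1 to 2 points with pairs.

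**The case against.** The best defense is that 9.5.3 is shorthand. It does not list the intervention effect either, and 9.5.2 does not spell out a clinic effect, yet nobody would conclude that those terms are absent. The opening word of the quoted phrase can be read as carrying the primary-model design handling forward. This stands in part: the paragraph does not forbid a block term, and a reader who infers that the sponsor has decided to leave it out goes further than the text. But the phrase also states how the design is controlled for, and block is not part of it. A statistician following it literally would fit the weaker model, and adding block later would look like a post hoc choice.

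Two other inferences are tempting and should be resisted. One is that the random clinic effect is the only adjustment; the count models also control for follow-up. The other is that utilization is the outcome most likely to differ by system and block. Section 3.4 says only that systems vary in general, and no section compares utilization with the other outcomes in this respect.

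It is also fair to say that the power figures rest on assumptions, that the simulation uses clinic means and not the logit or count models planned, and that sparse outcomes such as surgery could be a reason to limit block terms. All of this stands. It limits the size of the claim and calls for a fallback; it does not change the direction.

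**Conclusion.** The point holds as a gap in the SA3 model specification with a known direction and an unknown size. As written, the analysis is valid: the arm contrast is nearly unbiased and there is no excess false-positive risk. A reader might infer bias or a false claim of benefit; balanced allocation within block rules that out as a consequence of this omission. What is at risk is precision, through a conservative test and over-wide intervals for H3.

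In the illustration the effect on power runs from nothing (R = 0) to about 18 points (80% down to 62%, at ICC 0.05 and R = 70%), and to about 5 points (80% down to 75%) at ICC 0.01. These figures assume 48 clinics, 31 patients each, blocks of 4 and a normal approximation. They are not a forecast, because the documents give no utilization ICC, block size or variance share. No stated power is contradicted, since none is stated for H3, and H3 is secondary. The case for the change is the asymmetry: a possible loss of several points against a cost of about 1. It is a free improvement, not the repair of an error.

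**What to change.** In 9.5.3, add that the SA3 models control for block set, as for the primary outcomes, alongside the random clinic effects. Apply the same to the SA5 between-arm utilization comparisons.

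For outcomes too sparse to support the block terms, pre-specify a fallback to health system as the fixed effect. Give the fallback an objective trigger fixed before unblinding, for example non-convergence or a minimum number of pooled events per block term, so that the choice is not made outcome by outcome after the results are seen. If the sponsor prefers to leave block out, one sentence should say why.

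The cost is one or two sentences and some degrees of freedom (46 to 35 in the illustration with blocks of 4), worth about 1 point of power if blocks explain nothing. No new data are needed, because the block variable is already required for PA1 and PA2.

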## 10 Data collection and quality assurance

### 10.1 Data collection

- 10.1.1 **Baseline data:** Data collection for the three baseline patient questionnaires (Chronic LBP Questionnaire, STarT Back, and Oswestry) will be self-report via an internet-based form in a patient portal, a tablet-based form, or a paper questionnaire. The forms via patient portal or tablet will be loaded into the EMR. For paper questionnaires, the medical assistant will enter the data directly into the EMR. The PT checklist will be completed either electronically or on paper, and will also be loaded into the EMR.
- 10.1.2 **Follow-up data:** The study team will extract data from the EMR to determine 6-month assessment dates for enrolled patients. These data will be collected by the study team via telephone or e-mail, or as participant hard copy self-report returned to the project office, entered into a database, and matched with the EMR data.
- 10.1.3 **Medical resource utilization data:** Data for LBP-related use of medical resources during the 12-month assessment period will be collected for four of the five regional sites (Pittsburgh, Boston, Baltimore, and Salt Lake City). All four regional study sites participate in robust clinical research data networks (CRDNs). Boston Medical Center has access to the Clinical Data Warehouse of Boston University Medical Campus and Boston HealthNet, a partnership between Boston Medical Center, Boston University School of Medicine, and 15 community health centers that are participating in the study. Data from these resources will allow the capture of comprehensive information regarding the LBP-related medical resource utilization (e.g., office visits, specialty visits, tests, procedures, prescriptions, surgeries).
- 10.1.4 **Data sweeps:** The EMR administrators and programmers at each site have agreed to work with the study team to provide all necessary data. Reporting needed for the aims are related to data that need to be regularly pulled from the EMR and provided to practice managers and study personnel. These include:
- 1) Total numbers of subjects with LBP ICD-10 codes or who received care for back pain during the primary care clinic visit,
  - 2) Total numbers of subjects with completed data elements that include:
    - Chronic LBP Questionnaire
    - STarT Back Questionnaire
    - Oswestry LBP Questionnaire

All sites have agreed to program into the EMR the data elements above. They also agreed to program:

- 1) Bi-weekly sweeps of the EMR with a report that documents the ratio of completed data sets to total patients enrolled with LBP by clinic. These

will be used to assure appropriate recruitment levels at all sites. Reports will be directed to PCP champions and staff responsible for the clinic.

- 2) Regular reports from all of the EMRs of the data elements as well as the common data elements. These will be de-identified and sent to the coordinating site (Pittsburgh), where the Data Integrity Committee will work to harmonize all of the data integral to the primary aims of the study from the 5 sites.

## 10.2 Data management

10.2.1 **Data coordination and quality monitoring:** The University of Pittsburgh will manage data from the 5 regional sites' EMR teams. Monitoring of the trial will be facilitated through regular reports provided to the PIs and the Steering Committee. University of Pittsburgh staff have experience regularly running reports for other trials to monitor recruitment, enrollment, protocol implementation, attrition, and safety. They are also experienced with generating Data and Safety Monitoring Reports in both open and closed formats.

10.2.2 **Data source adequacy:** In choosing sites, major criteria were an established EMR linked with networked PCP clinics. All of the sites fit this criterion. One of the criteria for eligible PCP clinics was past volume of patients with LBP, identified by the ICD-9 code list. All sites conducted a data sweep representing calendar year 2013. In order to be an acceptable clinic site for the study, clinics needed to have a minimum of 400 patients with LBP diagnoses. Most of the selected clinics were far above that number. The conservative estimate is that that 10% of the 400 (40 per clinic) would be acute and high risk and therefore eligible, based on past literature for chronic rates, which range from 8-10%. In addition, a payer stakeholder, OPTUM, shared data with us based on first-time visits at primary care clinics across the country. Their analysis of chronicity (defined as 2 or more subsequent visits six months after the initial visit) verified a chronicity rate of <20%. Given the literature on chronic LBP and the STarT Back Tool, and data from OPTUM, 10% is a conservative estimate for a yearly yield of 31 patients per clinic.

## 10.3 Quality assurance

10.3.1 **Methods used to ensure unbiased and systematic data collection from all participants:** The major sources of potential bias in data collection with a cluster-RCT design lie in 1) the selection of sites and 2) missing or incomplete data collection once subjects are enrolled within a site. EMRs of all participating PCP clinics will be analyzed every two weeks for data completion rates (# completed data sets/total number of possible data sets). De-identified aggregate data completion rates will be provided to the site PI and feedback will be given to individual PCP clinics through the PCP site champion on a biweekly basis. The site PI for each city and the PCP clinic champions will meet regularly, using in person and teleconference visits as needed. During

these meetings recruitment, enrollment, retention, and data collection rates for the previous month and cumulative-to-date will be reviewed for each clinic and the city as a whole. Successes and challenges will be discussed in a spirit of quality improvement. This approach will allow sharing of best practices, successes, and challenges; rapid identification of potential barriers to optimal recruitment, retention, and data collection strategies; and rapid Plan-Do-Study-Act (PDSA) cycling to address barriers.

## **11 Participants rights and confidentiality**

### **11.1 Institutional Review Board (IRB) review**

This protocol and any subsequent modifications will be reviewed and approved by the relevant IRB for each study site. The University of Pittsburgh IRB as the IRB of Record for the UPMC and Intermountain Healthcare study sites has approved a waiver of informed consent/HIPAA authorization to access, record and use protected patient health information/patient medical record information for review and analysis of medical record data. It has also approved a waiver for the requirement to obtain a written informed consent for completion of questionnaires and interviews. Separate review and oversight will be conducted by the Boston University Medical Center IRB, Johns Hopkins University IRB, and Medical University of South Carolina IRB.

### **11.2 Informed consent scripts**

The letter to be mailed to QI participants informing them of the research data collection and scripts to be used for obtaining verbal consent are provided in Appendix 7 (6--month assessments).

### **11.3 Participant confidentiality**

Any data, forms, reports, and other records in the study database will be identified only by a unique participant identification number (Participant ID or PID) to maintain confidentiality. All hardcopy records will be kept in a locked file cabinet. All computer entry and networking programs will be done using PIDs only.

### **11.4 Study discontinuation**

The study may be discontinued at any time by the IRB or PCORI as part of their duties to ensure that research participants are protected.

## 12 Committees

The following committees will guide the work of this project:

- **Steering Committee:** made up of the project PI and Co-PI, site PIs, and patient co-investigators who will participate in monitoring the conduct of the project from its inception to the dissemination of the study results. Additional key co-investigators and staff from each of the study sites will also participate in Steering Committee conference calls and meetings.
- **Advisory Board:** this board is made up of a team of patient, provider, payer and purchaser representatives. The Advisory Board will provide a “safe harbor” for the Steering Committee members to review study options and provide input from their respective stakeholder perspective. The board will meet face-to-face as well as on conference calls and engage in meaningful and inclusive discussions of key issues as they emerge, particularly during the formative stages early in the granting period. Specifically, it will engage and advise the Steering Committee, be active ambassadors for the study, help with organization and planning, and directly participate in the dissemination phases the study.
- **Dissemination and Publications Committee:** this committee will promote, facilitate, and monitor TARGET Trial dissemination products and ensure compliance with PCORI dissemination policies.
- **Data Integrity Committee:** this committee will work to harmonize all of the data integral to the primary and secondary aims of the study from the five sites. This includes creating data dictionaries; data extraction templates, policies, and timelines; ensuring secure data housing; and working with the study statisticians to ensure the data is ready for analysis.

